#### 6.4.2 Secondary Efficacy Endpoints

The secondary efficacy endpoints are as follows:

- Mean change in BCVA score from baseline to Week 72 as assessed by ETDRS chart under low-luminance conditions
- Mean change in BCVA score from baseline to Week 72 as assessed by ETDRS chart

The secondary endpoints will be analyzed in a similar manner as the primary endpoint, using a linear mixed-effect model. Additional details regarding the analysis of secondary and exploratory efficacy endpoints will be provided in the DAP.

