## 1. BACKGROUND

## 1.1 BACKGROUND ON GEOGRAPHIC ATROPHY SECONDARY TO AGE-RELATED MACULAR DEGENERATION

Age-related macular degeneration (AMD) is the leading cause of irreversible blindness in people aged 50 years or older in the developed world (Friedman et al. 2004). The majority of the visual loss occurs in the advanced stage of AMD, which has two clinical forms: a non-exudative form, geographic atrophy (GA), which is characterized by loss of photoreceptors, retinal pigment epithelium (RPE), and choriocapillaris; and an exudative or wet form, known as neovascular AMD (nAMD), which is characterized by choroidal neovascularization (CNV) (Sunness et al. 1999; Lindblad et al. 2009). The prevalence of GA increases exponentially with age and approximately quadruples per decade beyond 50 years of age (Rudnicka et al. 2012). The estimated prevalence of GA in populations of European ancestry at 70 years of age is 0.70%, rising to 2.91% at 80 years of age and 11.29% at 90 years of age (Rudnicka et al. 2012).

In the early stages of GA, patients typically show minimal changes in central visual acuity (VA). However, while central VA may not yet be affected, patients often still experience significant symptoms from visual dysfunction, such as dense parafoveal scotomas (e.g., leading to difficulties with face recognition), delayed dark adaptation, reduced contrast sensitivity, and a decrease in reading rate (Sunness et al. 1995, 1999; Sunness and Applegate 1996). In the later stages, as the GA lesion expands into the fovea, a profound decrease in central VA occurs with a decline in activities of daily living (Lindblad and Clemons 2005). Moreover, GA is bilateral in most patients with advanced AMD (Sunness et al. 1999; Lindblad et al. 2009). As such, GA is a significant cause of both moderate and severe central visual loss.

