## 2.1.3 Exploratory Efficacy Objectives

The exploratory efficacy objectives for this study are as follows:

- To evaluate the efficacy of ITV injections of 20 mg FHTR2163 administered Q4W or Q8W in patients with GA secondary to AMD compared with sham control on the basis of the following endpoint:
  - Mean rate of change in the GA area, estimated based on GA area as measured by FAF at four timepoints: baseline, Week 24, Week 48, and Week 72
- To evaluate the efficacy of ITV injections of 20 mg FHTR2163 administered Q4W or Q8W in patients with foveal-involving GA and in patients with non-foveal-involving GA compared with sham control on the basis of the following endpoints:
  - Mean change in the GA area from baseline to Week 72 as measured by FAF
  - Mean rate of change in the GA area, estimated based on GA area as measured by FAF at four timepoints: baseline, Week 24, Week 48, and Week 72

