#### Ocular Inclusion Criteria: Study Eye

One eye will be designated as the study eye. If both eyes meet the following criteria, the eye with the worse VA and/or least function (as determined by the investigator and patient) will be selected for study treatment (study eye). If both eyes have the same visual function, the eye with the larger area of GA will be selected as the study eye.

 Visual acuity: BCVA letter score of ≥ 24 letters (Snellen equivalent of 20/320 or better) using ETDRS chart at starting distance of 4 m

If the study eye BCVA letter score is  $\geq$ 69 letters (Snellen equivalent of 20/40 or better), the non-study eye must have a BCVA letter score of  $\geq$ 44 letters (Snellen equivalent of 20/125 or better).

 Well-demarcated area of GA secondary to AMD with no evidence of prior or active CNV

- Prebaseline FAF image obtained via a Heidelberg platform 84–336 days prior to the screening visit that meets the following criteria:
  - Total GA lesion size must be ≥2.54 mm² (approximately ≥1 disc area [DA]) and ≤17.78 mm² (approximately ≤7 DA) and must reside completely within the FAF imaging field (Field 2–30 degree image centered on the fovea)

If GA is multifocal, at least 1 focal lesion must be  $\geq$  1.27 mm^2 (approximately  $\geq$ 0.5 DA).

 Presence of hyperautofluorescence of either banded or diffuse patterns adjacent to GA area

Note: Diffuse-trickling pattern is excluded.

- Baseline FAF image obtained during the baseline screening window (Day –30 to Day –1) must meet the following criteria:
  - Total GA lesion size must be ≥2.54 mm² (approximately ≥1 DA) and ≤25.4 mm² (approximately ≤10 DA) and must reside completely within the FAF imaging field (Field 2–30 degree image centered on the fovea).

If GA is multifocal, at least 1 focal lesion must be  $\geq$  1.27 mm^2 (approximately  $\geq$ 0.5 DA).

 Presence of hyperautofluorescence of either banded or diffuse patterns adjacent to GA area

Note: Diffuse-trickling pattern is excluded.

- Sufficiently clear ocular media, adequate pupillary dilation, and fixation to permit quality fundus imaging
- Ocular anatomy that would allow for safe and uneventful collection of approximately  $100~\mu L$  aqueous humor sample in the opinion of the investigator

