#### 6.1 DETERMINATION OF SAMPLE SIZE

This study is designed to evaluate the efficacy of FHTR2163 administered ITV Q4W and Q8W to patients with GA secondary to AMD. The focus of the efficacy outcome analyses will be on estimation of the magnitude of the treatment effect.

The primary efficacy endpoint is the mean change in GA area from baseline to Week 72 as measured by FAF. The sample size provides reasonable precision for estimation of the treatment effect with respect to the primary endpoint.

Approximately 360 patients will be randomized in a 2:1:1:1 ratio to one of four treatment groups: FHTR2163 Q4W, sham control Q4W, FHTR2163 Q8W, or sham control Q8W. Patients in the sham control Q4W and sham control Q8W groups will be pooled in the analyses.

Assuming a 15% dropout rate by Week 72 and a standard deviation of 1.82 mm² for change from baseline in GA area at Week 72 (estimated from the lampalizumab Phase II Study CFD4870g and the Phase III Studies GX29176 and GX29185), 114 patients in the FHTR2163 Q4W arm and 114 patients in the pooled sham-control group will provide 80% power to detect a targeted difference of 0.56 mm² (20% reduction relative to sham control) in the change from baseline in GA area at Week 72 between the FHTR2163 Q4W arm and the pooled sham-control arm. Calculations were based on two-sided t-test at the significance level of 20% and resulted in a total sample size of 285. No multiplicity adjustment is planned for this study.

A total of 131 patients had enrolled in this study as of 10 April 2020. As a result of the increase in missed visits, missed dosing, and missed assessments as a consequence of the COVID-19 pandemic, up to approximately 75 patients will be enrolled in addition to the originally planned 285 patients to help mitigate the potential impact on treatment effect and data.

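### The foveal/non-foveal split is planned for GA area but not for BCVA or low-luminance BCVA, so a null pooled vision result may be hard to interpret

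*Combined protocol and SAP*

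**What the plan says.** Section 6.4.2 names two secondary endpoints, change to Week 72 in BCVA and in low-luminance BCVA, both in the whole analysis population. On method it says: "The secondary endpoints will be analyzed in a similar manner as the primary endpoint, using a linear mixed-effect model".

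The primary model in Section 6.4.1 names HtrA1 carrier status, baseline lesion size and prior growth rate as covariates. It offers them as examples, not as a closed list. The same three factors stratify randomization (Section 4.2.1). Foveal status appears in neither place.

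Foveal status does appear in Section 2.1.3, which plans to evaluate efficacy "in patients with foveal-involving GA and in patients with non-foveal-involving GA compared with sham control". The endpoints listed there are change in GA area and rate of change in GA area. Neither acuity endpoint is listed, and the synopsis matches.

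The background in Section 1.1 says that central acuity changes little in early GA, and then: "In the later stages, as the GA lesion expands into the fovea, a profound decrease in central VA occurs".

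Entry (Section 4.1.1) requires a study-eye BCVA of at least 24 letters and sets no foveal criterion. When both eyes qualify, "the eye with the worse VA and/or least function (as determined by the investigator and patient) will be selected for study treatment". Further detail on secondary and exploratory analyses is left to the Data Analysis Plan, which is not among the documents.

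**The concern.** The plan will classify eyes by foveal involvement, but it lists that classification only for the anatomic endpoints. Its own natural history makes the fovea most directly relevant to central acuity. Both kinds of eye are expected, so the vision endpoints average over eyes that may be at different stages of acuity loss.

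BCVA and low-luminance BCVA are the only efficacy endpoints in Section 2.1 that measure function, and Section 3.3 presents lesion growth as a surrogate for vision loss. If a vision benefit sits mainly in one foveal group, the pooled mean understates it there. A pooled result near zero could then mean either no functional benefit or a benefit confined to part of the population. A foveal analysis of acuity chosen after the data are seen would carry less weight than one specified now.

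**Working it through.** **1. The plan's own figure (GA area only).** Section 6.1 gives "a standard deviation of 1.82 mm² for change from baseline in GA area at Week 72", a target difference of 0.56 mm², 80% power, a two-sided 20% test and 15% dropout.

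- Evaluable per group: 2 × (1.2816 + 0.8416)² × (1.82/0.56)² = 95.2, so 96.
- With dropout: 96/0.85 = 112.9, so 113, against 114 stated. With 114 × 0.85 = 96.9 evaluable, power is 80.4%.
- Total: 114 + 114 + 57 = 285.

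The figure reproduces to within one patient per group. It says nothing about vision: no effect, standard deviation or power is stated for BCVA.

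**2. What dilution could look like (assumptions).** Let a share f of eyes be able to show a vision effect and the rest show none. The pooled effect is then f times the effect in responsive eyes. Borrow the planned standardized effect, 0.56/1.82 = 0.308, and the current 144 per group (Q4W and pooled sham), or 144 × 0.85 = 122.4 evaluable. Two-sample t power at two-sided 20%:

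| Responsive share f | Pooled power | Power in the responsive stratum alone |
|---|---|---|
| 100% | 86.9% | 86.9% |
| 75% | 70.0% | 78.8% |
| 50% | 47.5% | 66.2% |
| 25% | 27.8% | 47.2% |

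The arithmetic is the same whichever foveal group responds.

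**3. What a foveal covariate would do (assumptions).** Take a foveal share p of 0.3 to 0.7, a gap d of 3 to 8 letters in 72-week change between foveal groups, and an SD of 12 to 15 letters. Variance explained is p(1 − p)d²/SD².

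- Low end: 0.21 × 9/225 = 0.008. High end: 0.25 × 64/144 = 0.111.
- Reduction in standard error: 1 − √(1 − 0.008) = 0.4%, up to 1 − √(1 − 0.111) = 6%.
- Chance imbalance in foveal share between groups: SE = √(0.25 × 2/122) = 0.064. At a 5-letter gap that is 0.3 letters, against a standard error for the treatment difference of 12 × √(2/122) = 1.5 to 15 × √(2/122) = 1.9 letters.

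The gain is in precision and is modest. A main-effect covariate leaves the pooled treatment effect essentially unchanged, so it does not address dilution. Only the subgroup estimates do.

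**4. How wide the subgroup intervals would be (same assumed SDs, half the eyes in each stratum).** For Q4W against pooled sham, with 61.2 evaluable per group, the 80% half-width is 1.2816 × SD × √(2/61.2), or 2.8 to 3.5 letters. For the pooled population it is 1.2816 × SD × √(2/122.4), or 2.0 to 2.5 letters.

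**The case against.** There are several fair points in favour of the plan as written.

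- **The direction is open.** Section 1.1 is general natural history and describes a transition. Eyes with GA still expanding within the fovea may be losing acuity, while eyes with GA far from it may lose little. A reader might infer that the BCVA result is diluted, or that the benefit must lie in fovea-sparing eyes. The documents support neither, since they give no acuity change by baseline foveal status. This stands, and it is a reason to report both groups.
- **The plan may yet use foveal status.** The covariate list is open, details are deferred to the Data Analysis Plan, and Sections 2.5 and 6.8 plan to relate imaging measures to efficacy and to look for predictors of response. A reader might infer that the plan ignores foveal status altogether. It does not, because GA area is to be examined by it. But Section 2.1.3 lists its endpoints and leaves acuity out, so that omission is in the text and is not merely deferred detail.
- **Low-luminance acuity.** Section 1.1 speaks of central acuity and does not mention this endpoint. Including it is an extension of the argument.
- **The existing covariates.** It is tempting to say that all three were chosen for area growth. Sections 3.3.2 and 3.3.5.3 say so for lesion size and prior rate. Section 3.3.5.4 gives carrier status a different rationale: genetic risk and response to treatment.
- **Stakes.** These are secondary endpoints in a study that Section 6.9 calls hypothesis-generating, with no vision power claimed. Subgroup estimates will be imprecise. This limits the weight of the point but does not remove the value of a cheap prespecified estimate.

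**Conclusion.** The point holds as a gap in prespecification. The protocol names no foveal adjustment or subgroup for either vision endpoint, although it plans the split for GA area and itself links profound central acuity loss to the fovea.

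The gap concerns sensitivity and interpretation. A reader might infer bias in the treatment comparison, but randomization keeps the pooled comparison unbiased in expectation.

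The size cannot be determined from the documents. The fall from 87% to about 48% power applies only if half the eyes respond, the other half show no effect, and the standardized effect equals the one planned for GA area. The 1 to 11% of variance rests on the assumed foveal share, letter gap and standard deviation.

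**What to change.** In Section 2.1.3 and the synopsis, add change in BCVA at Week 72 to the foveal/non-foveal exploratory objective, and by extension low-luminance BCVA. Report each active arm against pooled sham within each foveal group, as estimates with 80% confidence intervals.

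In Section 6.4.2, name baseline foveal involvement, graded by the masked reading center from screening images, as a covariate in both vision models. State that it is there for precision.

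The cost is wording in the objectives and the analysis plan. Section 2.1.3 already requires the classification, and the screening images already go to the reading center (Section 4.2.1), so no new visit, image or patient is needed. The downside is two more exploratory tables with wide intervals. They should be read as estimates: with two independent strata and no true effect, the chance that at least one 80% interval excludes zero is 1 − 0.8² = 36% for a single arm and endpoint.

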#### 6.5 SAFETY ANALYSES

The safety analysis population will consist of all randomized patients who received at least one FHTR2163 injection or sham control, with patients grouped according to treatment received. Safety summaries will be presented for all treated patients.

Safety will be assessed through descriptive summaries of adverse events, ocular assessments (e.g., inflammation, IOP, BCVA), clinical laboratory evaluation, ocular imaging, and immunogenicity against FHTR2163.

Verbatim descriptions of adverse events will be summarized by mapped term, appropriate thesaurus level, and toxicity grade (if applicable) (see Section 5.3.3).

#### 6.6 PHARMACOKINETIC ANALYSES

The PK analysis population will consist of any patient who has at least one FHTR2163 concentration data point. Individual and mean serum and aqueous humor FHTR2163 concentration versus time data will be tabulated and plotted by treatment arm. The serum and aqueous humor pharmacokinetics of FHTR2163 will be summarized by estimating total exposure (area under the concentration—time curve), maximum concentration, and elimination rate as data allow. Estimates for these parameters will be tabulated and summarized. Interpatient variability will be evaluated. Additional PK analyses will be conducted as appropriate.

#### 6.7 IMMUNOGENICITY ANALYSES

The immunogenicity analysis population will consist of all patients with at least one ADA assessment. Patients will be grouped according to treatment received or, if no treatment is received prior to study discontinuation, according to treatment assigned.

The numbers and proportions of ADA-positive patients and ADA-negative patients at baseline (baseline prevalence) as well as after drug administration (postbaseline incidence) will be summarized by treatment group.

The relationship between ADA status and efficacy, safety, and PK, endpoints may be analyzed and reported via descriptive statistics.

#### 6.8 BIOMARKER ANALYSES

The primary efficacy analysis described in Section 6.4 will be repeated in the HtrA1 risk-variant carrier and non-carrier subgroups as an exploratory analysis. Biomarkers will be analyzed together with PK data to explore PK/PD relationships. Additional analyses will be performed to identify biomarkers that are predictive of response to FHTR2163, are associated with rate of progression to a more severe disease state, are associated with susceptibility to developing adverse events, can provide evidence of FHTR2163 activity, or can increase the knowledge and understanding of disease biology.

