### Biomarker Objectives

The exploratory diagnostic biomarker objective for this study is to evaluate the efficacy as defined in the primary efficacy objective in carriers versus non-carriers of the high-temperature requirement A1 (HtrA1) AMD risk variant rs10490924.

The exploratory biomarker objective for this study is to identify and/or evaluate biomarkers that are predictive of response to FHTR2163, are associated with rate of progression to a more severe disease state, are associated with susceptibility to developing adverse events, can provide evidence of FHTR2163 activity, or can increase the knowledge and understanding of disease biology, on the basis of the following endpoints:

- Relationship between biomarkers in blood and aqueous humor and efficacy, safety, PK, immunogenicity, or other biomarker endpoints
- Relationship between retinal imaging measures (i.e., FAF, spectral domain optical coherence tomography [SD-OCT], optical coherence tomography angiography [OCT-A]) and efficacy, safety, PK, immunogenicity, or other biomarker endpoints

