### 2.5 BIOMARKER OBJECTIVES

The exploratory diagnostic biomarker objective for this study is to evaluate the efficacy of FHTR2163 as defined in the primary efficacy objective (see Section 2.1.1) in carriers versus non-carriers of the HtrA1 AMD risk variant rs10490924.

The exploratory biomarker objective for this study is to identify and/or evaluate biomarkers that are predictive of response to FHTR2163, are associated with rate of progression to a more severe disease state, are associated with susceptibility to developing adverse events, can provide evidence of FHTR2163 activity, or can increase the knowledge and understanding of disease biology, on the basis of the following endpoints:

 Relationship between biomarkers in blood and aqueous humor (listed in Section 4.5.8) and efficacy, safety, PK, immunogenicity, or other biomarker endpoints  Relationship between retinal imaging measures (e.g., FAF, SD-OCT, optical coherence tomography angiography [OCT-A]) and efficacy, safety, PK, immunogenicity, or other biomarker endpoints

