## 3.3.5.4 Rationale for HtrA1 Risk-Variant Genotyping Assay

Patients will be stratified at enrollment on the basis of carrier versus non-carrier status using the HtrA1 risk-variant genotyping assay for the single nucleotide polymorphism rs10490924 (see Appendix 3). rs10490924 is established as one of the most significant genetic risk factors for advanced AMD (Fritsche et al. 2016) and the response to FHTR2163 treatment will be evaluated in carrier versus non-carrier subgroups.

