#### 6. STATISTICAL CONSIDERATIONS AND ANALYSIS PLAN

The analysis of data for the 76-week study period will be performed when all randomized patients have either completed the 76-week study period or have discontinued from the study prior to Week 76, all data from this period are in the database, all data have been cleaned and verified, and the database is locked.

Detailed specifications of the statistical methods will be described in the DAP.

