#### 6.4.1 Primary Efficacy Endpoint

The primary efficacy endpoint is the mean change in GA area from baseline to Week 72 as measured by FAF.

Comparison of each active arm versus the pooled sham-control arm will be assessed using a linear mixed-effect model with an effect for treatment and with covariate adjustments for baseline factors such as HtrA1 risk-variant carrier status, baseline GA lesion size, and annualized prebaseline GA progression rate. The primary analysis will be based on all available data up to 72 weeks, with no imputation for missing data. Two-sided 80% confidence interval will be provided for the estimated treatment effects. Hypothesis testing will be conducted at the two-sided significance level of 20%, and no multiple-testing adjustment is planned.

Detailed specifications of the statistical methods will be described in the DAP.

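### Low-severity improvement: for the carriers-versus-non-carriers objective, section 6.8 names only the primary analysis repeated in each subgroup; it could also state the difference between the two treatment effects with its 80% CI, unless the DAP already does

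*Combined protocol and SAP*

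**What the plan says.** The synopsis sets an exploratory diagnostic biomarker objective, to "evaluate the efficacy as defined in the primary efficacy objective in carriers versus non-carriers". Section 2.5 repeats it with the words "in carriers versus non-carriers of the HtrA1 AMD risk variant rs10490924". Section 3.3.5.4 puts it slightly differently: "the response to FHTR2163 treatment will be evaluated in carrier versus non-carrier subgroups".

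For the analysis, section 6.8 says that the primary efficacy analysis "will be repeated in the HtrA1 risk-variant carrier and non-carrier subgroups as an exploratory analysis". The primary analysis in section 6.4.1 is a linear mixed-effect model of each active arm against pooled sham. Carrier status is one of its covariates, and no treatment-by-carrier term is stated. It gives a two-sided 80% CI, and "Hypothesis testing will be conducted at the two-sided significance level of 20%, and no multiple-testing adjustment is planned".

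Section 6.8 also promises further work on biomarkers that predict response, but that sentence names neither a method nor carrier status.

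Detail is deferred. Section 6 says "Detailed specifications of the statistical methods will be described in the DAP", and section 6.4.2 says "Additional details regarding the analysis of secondary and exploratory efficacy endpoints will be provided in the DAP". The DAP is not among the documents.

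**The concern.** Efficacy in carriers versus non-carriers has two natural readings. One is the treatment effect shown separately in each subgroup, which section 6.8 delivers. The other is how far the two effects differ, for which no estimate is named. Section 6.1 says "The focus of the efficacy outcome analyses will be on estimation of the magnitude of the treatment effect", so it is odd that the comparison named in this objective has no stated estimate.

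The practical risk is one of interpretation. Two subgroup tests side by side at 20% invite the conclusion that the drug works in one subgroup and not in the other whenever one crosses the threshold and the other does not. That pattern is common even when the true effect is identical in both, because each subgroup has lower power than the whole comparison and the smaller subgroup has the least. A direct contrast, prespecified, answers the comparative question and shows how uncertain the answer is.

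**Working it through.** **Inputs from the plan.** Section 6.1: target difference 0.56 mm², SD 1.82 mm², 15% dropout, two-sided alpha 0.20, 80% power, 114 patients each in Q4W and pooled sham, total 285. Section 3.1: enlarged arms of 144 (Q4W), 72 (Q8W) and 144 (pooled sham).

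**Inputs assumed.** Carrier share p of 50-80%, and variance explained by covariates (R²) of 0-40%. Neither is in the documents. Carrier share is taken as equal across arms, which the stratification supports, and the SD as equal in both subgroups.

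**The plan's own figure.** The two-sample formula gives 96 evaluable per group, and 96/0.85 = 113 against the stated 114. At 114 × 0.85 = 96.9 evaluable per group, noncentral-t power is 80.4%. Under 2:1:1:1 allocation, 114 × 5/2 = 285. The stated design reproduces.

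**How often the two subgroup tests disagree with no true difference.** Evaluable patients are 144 × 0.85 = 122.4 (Q4W, pooled sham) and 72 × 0.85 = 61.2 (Q8W). In a subgroup with fraction f of the patients, SE = 1.82 × √(1−R²) × √(1/(n₁f) + 1/(n₂f)). The subgroups share no patients, so

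P(exactly one significant) = P_c(1−P_n) + P_n(1−P_c),

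where P_c and P_n are the powers in carriers and non-carriers at 0.56 mm².

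Worked case: Q4W, 70% carriers, R² 0.
- Carriers: SE = 1.82 × √(2/85.68) = 0.278; power 77%.
- Non-carriers: SE = 1.82 × √(2/36.72) = 0.425; power 52%.
- Exactly one significant: 0.767 × 0.484 + 0.516 × 0.233 = 49%.

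With no effect in either subgroup the figure is 2 × 0.2 × 0.8 = 32%.

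**The direct contrast.** SE = 1.82 × √(1−R²) × √[(1/n₁ + 1/n₂)(1/p + 1/(1−p))], and the 80% half-width is 1.2816 × SE. In the worked case SE = √(0.278² + 0.425²) = 0.508, so the half-width is 0.65 mm². Power for a true carrier difference of 0.56 mm² is Φ(0.56/0.508 − 1.2816) plus a small opposite tail, 44%. With equal effects the contrast is significant in 20% of trials by construction.

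Ranges over carrier shares of 50-80%:

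| | Exactly one subgroup significant, equal effects | Contrast 80% half-width (mm²) | Contrast power for 0.56 mm² |
|---|---|---|---|
| Q4W, R² 0 | 45-55% | 0.60-0.75 | 39-48% |
| Q4W, R² 40% | 30-46% | 0.46-0.58 | 49-61% |
| Q8W, R² 0 | 50-55% | 0.73-0.91 | 33-39% |
| Q8W, R² 40% | 43-54% | 0.57-0.71 | 41-50% |

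At R² 25% the disagreement rates lie between or level with these: 37-51% (Q4W) and 47-55% (Q8W).

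**What the contrast does when the tests disagree.** In simulation (400,000 trials per scenario, Q4W, equal true effects), among trials with exactly one significant subgroup the contrast was also significant in about 25-37% at R² 0 and 25-45% at R² 40%. These are false positives, since the effects are equal. They exceed 20% because disagreement selects trials in which the two estimates happen to lie apart.

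**The case against.** The case against acting is a fair one. The objective is exploratory, in a study that section 6.9 calls hypothesis-generating. Section 6.8 does what section 3.3.5.4 promises. The subgroups are disjoint and reported with intervals, so a reader can approximate the difference from the two CIs. The sentence in 6.8 on predictive biomarkers may be meant to include such a comparison. The contrast is weak: in most scenarios its half-width exceeds the whole 0.56 mm² target.

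Most of this stands, and it sets the severity. It does not remove the point. The predictive-biomarker sentence names no method and does not mention carrier status. A derived difference leaves the model unstated, including its time terms. A wide interval shows the uncertainty that two separate test results conceal.

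Three stronger readings are tempting, and the documents support none of them.
- A reader might infer that the plan omits the contrast altogether. Sections 6, 6.4.1 and 6.4.2 defer methods to the DAP, so this cannot be known.
- A reader might infer that significance in carriers alone would drive a decision. No section ties one to it. Section 3.3.5.2 states only a general aim of finding likelier responders for future studies.
- A reader might infer that the contrast protects against a false carrier story. It does so only partly: in the very trials where the subgroup tests disagree by chance, it would itself mislead in about 25-45% (Q4W).

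**Conclusion.** The point holds as an optional improvement of low severity, not as an error. The documents name two subgroup effects for this objective and no estimate of their difference. With the same true effect of 0.56 mm² in both subgroups, the subgroup tests would disagree in about 30-55% of Q4W and 43-55% of Q8W comparisons, against a 20% false-positive rate for a direct contrast.

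The size rests on the assumed carrier share and R². The lower disagreement rates belong to balanced carrier shares and strong covariates, and sections 3.3.2 and 3.3.5.3 give reason to expect that prior growth rate is a strong covariate. The design and primary result are unaffected, and the point falls away if the DAP already specifies the contrast.

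**What to change.** In section 6.8, and in the DAP if it is not there:

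- Add a treatment-by-carrier term to the primary model, by time where the model has time terms.
- For each active arm versus pooled sham, report the carrier minus non-carrier difference in the Week 72 treatment effect with its 80% CI, as the exploratory analysis for this objective.
- Keep the within-subgroup estimates and 80% CIs as descriptive.
- State that the contrast is read as an estimate with its interval, and that a non-significant contrast is not evidence of no difference.

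If the DAP already does this, a cross-reference in 6.8 is enough.

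The cost is one or two sentences. No patients, visits or data are added, because carrier status is already a stratification factor and a covariate. The price is an imprecise result: 80% half-widths of about 0.46-0.75 mm² for Q4W and 0.57-0.91 mm² for Q8W.
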